9.2.4.2 Serious adverse events

For reporting of serious adverse events we will adhere to the ICH E2A guidelines (18) and define a serious adverse event (experience) or reaction 'as any untoward medical occurrence that at any dose results in death, is life-threatening, requires inpatient hospitalisation or prolongation of existing hospitalisation, results in persistent or significant disability/incapacity, or is a congenital anomaly/birth defect. Exemptions will be SARS-CoV-2 related deaths or SARS-CoV-2 related hospitalisations, which are among the assessed clinical outcomes. The term "life-threatening" in the definition of "serious" refers to an event in which the patient was at risk of death at the time of the event; it does not refer to an event which hypothetically might have caused death if it were more severe'.

9.2.4.3 Laboratory parameters

Laboratory parameters besides immune response parameters will be assessed at bi-annually cohort visits according to the cohort protocols.

9.2.4.4 Vital signs

Not relevant for purpose of this trial.

9.2.5 Assessments in participants who prematurely stop the study

All clinical outcomes will be assessed from routinely collected cohort data which will also be available if patients decide to prematurely stop participating in the clinical trial.

9.2.6 Assessments in participants who prematurely stop the study

We refer to the master protocol

9.3 Procedures at each visit

9.3.1 Eligibility (and eventual enrolment, randomisation)

We refer to the master protocol.

9.3.2 Enrolment and randomisation

We refer to the master protocol.

9.3.3 Follow-up 1 week 12

We refer to the master protocol.

9.3.4 Follow-up 2 week 48

We refer to the master protocol.

10. SAFETY

10.1 Drug studies

10.1.1 Reporting of serious adverse events (SAE) and other safety related events

We refer to the master protocol.

In addition to reporting of all SAE to the sponsor / principle investigators according to the rules set by Swissmedic all study physicians must report SAE via the EIViS (Elektronisches Vigilance-Meldesystem)

to Swissmedic (<https://www.swissmedic.ch/swissmedic/de/home/services/egov-services/elvis.html>). All study physicians must register at ELViS.

10.1.2 Follow up of (Serious) Adverse Events

We refer to the master protocol.

11. STATISTICAL METHODS

11.1 Hypothesis

To compare the effectiveness in term of serological immune response of approved SARS-CoV-2 vaccines in immunocompromised patients, we aim to demonstrate that the second vaccine available in the market is no worse than the comparator by more than 10%. Therefore, we formulate the null hypothesis $H_0: \pi_1 \geq \pi_2 + 10$ versus the alternative hypothesis $H_1: \pi_1 - 10 < \pi_2$. The choice of a non-inferiority margin of 10% relies on expert opinion/clinical judgment.

11.2 Determination of Sample Size

Phase 1 to Phase 3 trials of COVID-19 mRNA Vaccine Moderna® and Comirnaty® (Pfizer / BioNTech) report immunological response titers that are not comparable due to the different assays that were used. Moderna uses an in-house developed ELISA assay, while Pfizer / BioNTech uses an in-house developed Luminex assay. However, currently available results show that titers are high at 4 weeks post vaccination and the proportion of patients that is reactive to vaccination is close to 100 percent (19, 20). However, no data is available for an immunocompromised population such as the one in our study. By assuming vaccine reactivity of 90% in both vaccine groups, we power our non-inferiority trial such that a 95% two-sided confidence interval excludes a difference in favour of the reference group of more than 10%. A sample size of 380 (190 in each treatment arm) is required for a statistical power of 90% and a type I error of 0.025. We believe that a target sample of 380 patients participants is feasible, which represents 32 patients distributed across 6 participating centres. Sample size was calculated using the “ssc_propcomp” function of the R statistical software package “SampleSize4ClinicalTrials’ (21).

11.3 Statistical criteria of termination of trial

Not applicable. No interim analysis is planned during the pilot trial and termination will not be based on any statistical criteria.

11.4 Planned Analyses

11.4.1 Datasets to be analysed, analysis populations

We refer to the master protocol

11.4.2 Feasibility analysis

We refer to the master protocol.

11.4.3 Analyses of immunological and clinical outcomes

Immunological outcomes at baseline and 12-week follow-up will be reported as frequency and percentage of positive serologic immune response for both vaccine arms. The primary objective is to assess the non-inferiority of the second licensed vaccine *versus* the first licensed vaccine in regards to the presence of pan-IgG antibody, as measured by the Elecsys® Anti-SARS-CoV-2 S immunoassay. Difference in primary outcome among the two vaccine arms will be assessed by a two-sided 95% confidence interval, showing a credible range for the true difference between the second licensed vaccine and the first licensed vaccine. Non-inferiority will be established at the α significance level, if the lower limit of a 95% two-sided Wald confidence interval for the difference (second licensed– first licensed) is above -10% , where 10% is the pre-defined non-inferiority margin.

We will report frequency and percentage of positive serological immune response for both vaccine arms among different pre-specified subgroups of patients most prone to complicated infections with SARS-CoV-2. These are for HIV positive individuals, patients with less than 200 CD4cell/ μ L, unsuppressed HI viral load, male gender, age group 60 to 69, 70 older and history of cardiovascular diseases or present metabolic syndrome. For transplanted individuals these are patients with less than 200 CD4cell/ μ L, intense versus less intense immunosuppressive therapy, male gender, age group 60 to 69, 70 older and

history of cardiovascular diseases or present metabolic syndrome.

A secondary and tertiary analysis will assess the non-inferiority of the second licensed vaccine *versus* the first licensed vaccine in regards to the presence of anti-Nucleocapsid (N), as measured by the Elecsys® Anti-SARS-CoV-2 N assay and the presence of IgM, IgA and IgG as measured by the ABCORA 2.0 assay.

Clinical outcomes related to COVID-19 infection at 48 weeks and patient reported COVID-19 infection of household members will be reported as frequency with percentage for the different treatment arms.

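### The Wald interval behind the primary non-inferiority rule runs slightly above the stated 0.025 error, by more only if both cohorts respond well; a score-type interval is a cheap improvement

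*Combined protocol and SAP*

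**What the plan says.** All of this is in the Combined protocol and SAP (the first sub-protocol) unless stated otherwise.

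- Section 11.4.3 makes the primary decision on the difference in response, second licensed minus first licensed vaccine. Non-inferiority is declared "if the lower limit of a 95% two-sided Wald confidence interval for the difference" is above -10%, "where 10% is the pre-defined non-inferiority margin".
- Section 11.2 sizes the trial "By assuming vaccine reactivity of 90% in both vaccine groups". It gives 380 patients, 190 per arm, and says this number "is required for a statistical power of 90% and a type I error of 0.025".
- The same section reports that in earlier trials "the proportion of patients that is reactive to vaccination is close to 100 percent", and then that "no data is available for an immunocompromised population such as the one in our study".
- Section 6.1 has the minimisation run separately in the HIV and transplant cohorts.

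The text available gives no score-type or exact interval as an alternative and no sensitivity analysis of the interval method. Several analysis topics are deferred to the master protocol, which was not available to check.

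**The concern.** The Wald interval estimates its standard error from the observed proportions. Near 100% response that estimate is often too small, most of all when the two arms happen to look alike. For a non-inferiority test the result is one-directional: the lower limit clears -10% too often when the second vaccine really is 10 points worse. The plan commits to an error of 0.025 while saying that it has no data on where response will fall in this population, and the earlier trials it cites sit in the range where the Wald interval performs worst. At stake is whether the stated error for the primary conclusion holds over the range of response rates the trial could meet.

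**Working it through.** **Inputs.** Margin 0.10, one-sided error 0.025, power 0.90, response 0.90 in both arms, 190 per arm (sections 11.1, 11.2 and 11.4.3). For the cohort mix: 430 randomised, 352 from the HIV cohort and 78 from the transplant cohort (Protocol, section 7.1). An equal split is assumed: 215 per arm, made up of 176 and 39.

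**Step 1: the plan's own figure.** With unpooled variance,

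n per arm = (1.960 + 1.282)² × (0.9×0.1 + 0.9×0.1) / 0.10² = 10.507 × 0.18 / 0.01 = 189.1, rounded up to 190, so 380 in total.

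This matches section 11.2. Exact power of the Wald rule at 90% in both arms is 0.900, as stated.

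**Step 2: exact error, homogeneous arms.** Let x₁ and x₂ be the responders on the first and second licensed vaccine, and d = x₂/190 − x₁/190. The error is the sum over all (x₁, x₂) of

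Bin(x₁; 190, p) × Bin(x₂; 190, p − 0.10) × 1[lower limit > −0.10].

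The Wald lower limit is d − 1.96 × √(p̂₁(1−p̂₁)/190 + p̂₂(1−p̂₂)/190). Newcombe replaces the second term by √((p̂₂−l₂)² + (u₁−p̂₁)²), where l₂ and u₁ are Wilson limits. Miettinen-Nurminen uses the variance estimated under the constraint that the difference equals −0.10.

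| Reference vs second vaccine | Wald | Newcombe | Miettinen-Nurminen |
|---|---|---|---|
| 90% vs 80% | 2.67% | 2.55% | 2.40% |
| 95% vs 85% | 3.00% | 2.45% | 2.35% |
| 98% vs 88% | 3.66% | 2.30% | 2.15% |
| 99% vs 89% | 3.97% | 2.17% | 2.15% |

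At 215 per arm the Wald figures are 2.68%, 3.09%, 3.48% and 3.80%, so the larger number randomised does not remove the excess.

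**Step 3: exact error, two cohorts balanced between arms.** Responders in each arm are now the sum of two binomials, 176 HIV and 39 transplant. The second vaccine is 10 points worse in each cohort, and the pooled Wald rule is applied unchanged.

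| HIV / transplant response, reference arm | Overall | Wald error |
|---|---|---|
| 99% / 50% | 90% | 1.1% |
| 99% / 60% | 92% | 1.6% |
| 99% / 70% | 94% | 2.2% |
| 99% / 80% | 96% | 2.8% |
| 100% / 90% | 98% | 3.4% |

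The reason shows in the first row. The overall rates are (176×0.99 + 39×0.50)/215 = 0.901 and 0.801.

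- Pooled Wald standard error: √((0.901×0.099 + 0.801×0.199)/215) = 0.0340.
- Standard error with cohort sizes fixed: √((176×0.99×0.01 + 39×0.50×0.50 + 176×0.89×0.11 + 39×0.40×0.60)/215²) = √(38.08/46,225) = 0.0287.

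The Wald rule includes between-cohort variation that the balanced allocation has already removed, so it is conservative.

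**Step 4: cost in power at 190 per arm.**

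| Response in both arms | Wald | Newcombe | Miettinen-Nurminen |
|---|---|---|---|
| 90% | 0.900 | 0.890 | 0.884 |
| 95% | 0.992 | 0.986 | 0.985 |
| 98% | 1.000 | 1.000 | 1.000 |

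**The case against.** The strongest reply is that the high-response scenarios do not describe this trial. The near-100% figure in section 11.2 concerns earlier trials in other populations, and the plan itself works at 90%, where Wald (2.67%) and Newcombe (2.55%) hardly differ. The Protocol (third sub-protocol, section 4.1) later reports that people with HIV mostly responded, while many transplant recipients did not. With 352 and 78 patients and every HIV patient responding, an overall 98% would need (0.98×430 − 352)/78 = 89% response among transplant recipients, 99% would need 94%, and 95% would need 72%. Under that mix the Wald rule is conservative, as step 3 shows. The rule is also prespecified and consistent with the sample size calculation.

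Most of this stands. It removes the 3.7% to 4.0% figures as a description of the trial and leaves them as a limiting case. It does not remove the small excess at the planning rate with homogeneous arms. Nor was the transplant result known when the rule was written: the plan says it had no data, and a prespecified rule should hold its error over the range that could have occurred.

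A reader might make two stronger inferences. One is that the primary conclusion was tested at about 4%; that needs homogeneous response at 98% to 99%, which the documents make unlikely. The other is that a zero-width interval, if both arms reach 100%, is an error in the rule. It changes no decision: Newcombe would then give a lower limit of −3.84/(190 + 3.84) = −2.0 points, which also clears −10%.

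**Conclusion.** The point holds as a modest one. With homogeneous arms of 190, the Wald rule's one-sided error is 2.7% at the planning rate and 3.0% at 95% against 85%, compared with the stated 2.5%. It reaches 3.7% to 4.0% only with response of 98% to 99% in both cohorts. With cohorts balanced between arms and HIV response at 99%, the error is 1.1% to 2.2% for transplant response of 50% to 70%, and exceeds 2.5% only from about 80%. The cohort figures assume the 352/78 mix, an equal split and a 10-point deficit in each cohort. The sample size of 380 reproduces. Nothing here shows that the non-inferiority conclusion reported in the Protocol would change. This is an inexpensive improvement, not a demonstrated failure of error control.

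**What to change.** In section 11.4.3, base the -10% rule on a Miettinen-Nurminen or Newcombe 95% interval for the difference and name the method. The Protocol describes this sub-study as completed, so where the primary analysis is already done, report that interval beside the prespecified Wald result instead of replacing it.

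In section 11.2, restate power at 380 patients and 90% response as about 88% (Miettinen-Nurminen) to 89% (Newcombe).

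The cost is a short text change and 1.0 to 1.6 points of power at 90% response, with less than one point lost at 95% or above. Restoring 90% exactly would take about 198 to 200 per arm, but no increase is needed: at 215 per arm, Newcombe power at 90% response is 0.923, assuming an equal split and all patients analysed. Neither interval is exact everywhere (Newcombe is at 2.78% at a 60% reference rate), but both stay close to 2.5% or below from the planning rate upward.

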5.1 Immunological Outcomes

The primary immunological endpoint are antibodies to the SARS-CoV-2 spike (S1) protein receptor binding domain (RBD) in human serum and plasma assessed by the commercial immunoassay

Elecsys® Anti-SARS-CoV-2 S for the in vitro quantitative determination (15). This assay detects pan-Ig antibody response (pan-Ig anti-S1-RBD) and allows for a quantitative assessment of the serological response of the participants at baseline and three months after vaccination. Additionally, we will qualitatively measure anti-Nucleocapsid (N) responses with Elecsys® Anti-SARS-CoV-2 N assay to gain a broader insight on the immune response of the participants.

In addition SARS-CoV-2-binding antibody responses of the participants by analyzing the IgM, IgA and IgG responses to a wider range of SARS-CoV-2 proteins (S1, S2, RBD and N using an in-house method (ABCORA 2.0) established at the Institute of Medical Virology (IMV), UZH) will be measured. The ABCORA 2.0 test has an advantage over commercial available tests, as it allows a parallel assessment of IgG, IgM and IgA reactivity to multiple antigens enabling a high-dimensional temporal resolution of antibody responses and a dissection between humoral responses to an infection and vaccination

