5.2 Clinical Outcomes

The clinical effectiveness endpoints are (according to FDA recommendations for phase III Covid-19 vaccine licensing trials (14)) the following:

- Newly PCR-confirmed asymptomatic COVID-19 infection (identified by the presence of anti-SARS-CoV-2 nucleocapsid antibodies or SARS-Cov-2 PCR or rapid antigen test) and no related symptoms [(i.e. fever or chills, cough, shortness of breath or difficulty breathing, fatigue, muscle or body aches, headache, new loss of taste or smell, sore throat, congestion or runny nose, nausea or vomiting, and diarrhea)] at any time point in within 48 weeks following randomisation.
- Newly PCR-confirmed symptomatic COVID-19 infection with at least one of the following symptoms (i.e. fever or chills, cough, shortness of breath or difficulty breathing, fatigue, muscle or body aches, headache, new loss of taste or smell, sore throat, congestion or runny nose, nausea or vomiting, and diarrhea at any time point in within 48 weeks following randomisation
- severe COVID-19 infection with respiratory failure, evidence of shock (as diagnosed by a treating physician), clinically significant acute renal, hepatic, or neurologic dysfunction; admission to an intensive care unit; and death at any time point in within 48 weeks following randomisation.
- COVID-19 burden of diseases (BOD), a composite of the above endpoints. The BOD is will be scored as by using 0 for no COVID-19, 1 for non-severe COVID-19, and 2 for severe COVID-19.

An additional clinical effectiveness endpoint is patient reported asymptomatic or symptomatic infections of household members.

All clinical outcomes will be measured in the trial database during a follow-up period of 48 weeks after randomisation and vaccination.

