7.1 Eligibility criteria

Inclusion and exclusion criteria as defined in the master protocol:

Inclusion criteria:

- All patients with either a chronic HIV infection or recipients of solid organs registered with informed consent from the SHCS and STCS cohorts aged ≥ 18 years
- Patients with solid organ transplantation of lungs or kidneys at least one month post-transplantation with a prednisone dose of 20mg or less.
- Additional consent for participation in the pilot trial
- Covid-19 vaccination recommended by treating physician

Exclusion criteria:

- Pregnancy
- Acute symptomatic SARS-CoV-2 infection, influenza or other acute respiratory tract infection
- Known allergy or contra-indications for vaccines or any vaccine components
- Any emergency condition requiring immediate hospitalization for any condition
- Patients with previous PCR documented SARS-CoV-2 infection and, or documented antibodies less than 3 months prior to randomisation
- Patients with solid organ transplantation (lung or kidney) with the following conditions:
 - Solid organ transplant recipients less than one month post-transplantation
 - Solid organ transplant recipients with the use of T-cell depleting agents in the last 3 months (i. e induction treatment in standard risk or high-risk immunological situation or rejection treatment).
 - Solid organ transplant recipients with the need of pulse corticosteroids (>100 mg prednisone or equivalent) in the last 1 month or rituximab in the last 6 months
 - Solid organ transplant recipients with the need of any kind of chemotherapy treatment

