8.1.1 Experimental Intervention (treatment / medical device)

ICH: Name and description of the investigational product(s).

The COVID-19 mRNA Vaccine Moderna® is a white to off-white, sterile, preservative-free frozen suspension for intramuscular injection. The vaccine contains a synthetic messenger ribonucleic acid (mRNA) encoding the pre-fusion stabilized spike glycoprotein (S) of SARS-CoV-2 virus. The vaccine also contains the following ingredients: lipids (SM-102, 1,2-dimyristoyl-rac-glycerol-3-methoxypolyethylene glycol-2000 [PEG2000-DMG], cholesterol, and 1,2-distearoyl-sn-glycerol-3-phosphocholine [DSPC]), tromethamine, tromethamine hydrochloride, acetic acid, sodium acetate, and sucrose. The COVID-19 mRNA Vaccine Moderna® (100 µg) is administered intramuscularly as a series of two doses (0.5 mL each), given 28 days apart. The vaccine is injected in the deltoid muscle.

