9.2.2 Assessment of immunological endpoints

We will assess pan-IgG anti S (RBD) (quantitative) and anti- N antibodies (qualitative) with the commercial Elecsys® Anti-SARS-CoV-2 tests at baseline and at 12 weeks following randomisation and vaccination (primary immunological endpoint).

We will assess SARS-CoV-2-binding antibody responses of the participants by analyzing the IgM, IgA and IgG responses to a wider range of SARS-CoV-2 proteins (S1, S2, RBD and N using an in-house method (ABCORA2.0) established at the Institute of Medical Virology (IMV), UZH (secondary immunological endpoint). The ABCORA 2.0 test allows for a parallel assessment of IgG, IgM and IgA reactivity to multiple antigens enabling a high-dimensional temporal resolution of antibody responses and a dissection between humoral responses to an infection and vaccination. We expect that the ABCORA2.0 antibody test will be more sensitive than the Elecsys® Anti-SARS-CoV-2 S antibody test.

Patients will be invited to see their treating physician 12 weeks after randomisation (see Study schedule). During baseline and follow-up visits this visit a blood sample will be taken (EDTA blood (2 x 7.5 ml)) and assessed for the above listed antibodies:

- 1ml for Elecsys® Anti-SARS-CoV-2 N and S tests (performed locally at each laboratory)
- 2ml EDTA Plasma for ABCORA 2.0 test (performed at IMV, UZH)

EDTA blood should be processed within 24h and EDTA plasma should be stored at -20°C. For ABCORA 2.1 antibody measurements plasma samples will be collected at each center and a collective shipment will be sent after baseline and at 12 weeks after randomisation and vaccination to the IMV, UZH. One sample will be stored according to SHCS and STCS protocols for later eventual analyses at the centers of University Hospital Zurich.

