9.2.3 Assessment of clinical endpoints

Patients are informed to contact center physicians in case an asymptomatic or symptomatic SARS-Cov-2 infections was diagnosed outside the settings of participating cohort centers. Clinical endpoints will be assessed at 12 and 48 weeks, and during each cohort visits, that fall in between the trial specific visit dates.

- Newly PCR-confirmed asymptomatic Covid-19 infection (identified by the presence of anti-SARS-CoV-2 nucleocapsid antibodies, or PCR or rapid antigen test) and no related symptoms [(i.e. fever or chills, cough, shortness of breath or difficulty breathing, fatigue, muscle or body aches, headache, new loss of taste or smell, sore throat, congestion or runny nose nausea or vomiting, and diarrhea)] at any time during the 48 weeks of follow-up

During all visits at the trial centres (study specific at 12 and 48 weeks, as well as cohort visits) a PCR SARS-COV-2 test will only be conducted if the treating physician would also conduct such a test during clinical routine (e.g. exposure to infected individual). PCR tests done in between independently will be recorded with dates and results. In case of a positive test result, physicians will check for symptoms and patients will be followed-up according to clinical routine and physicians' judgement.

- Newly PCR-confirmed symptomatic Covid-19 infection with at least one of the following symptoms (i.e. fever or chills, cough, shortness of breath or difficulty breathing, fatigue, muscle or body aches, headache, new loss of taste or smell, sore throat, congestion or runny nose nausea or vomiting, and diarrhea) at any time during the 48 weeks of follow-up

During all visits at the trial centres (study specific at 12 and 48 weeks, as well as cohort visits) a PCR SARS-COV-2 test will only be conducted if the treating physician would also conduct such a test during clinical routine (e.g. COVID-19 related symptoms; exposure to infected individual). In case of a positive test result, physicians will check for symptoms and patients will be followed-up according to clinical routine and physicians' judgement.

- Severe COVID-19 infection with respiratory failure, evidence of shock (as diagnosed by a treating physician), clinically significant acute renal, hepatic, or neurologic dysfunction; admission to an intensive care unit; or death at any time during the 48 weeks of follow-up.

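### The plan tests non-inferiority on presence of anti-nucleocapsid antibody, which it elsewhere uses to identify infection, with no margin or direction stated for that test

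*Combined protocol and SAP*

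**What the plan says.** All section references are to the Combined protocol and SAP (first sub-protocol) unless noted.

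- **The analysis.** Section 11.4.3 plans secondary and tertiary non-inferiority analyses of the second against the first vaccine: one "in regards to the presence of anti-Nucleocapsid (N), as measured by the" Elecsys N assay, the other on IgM, IgA and IgG by ABCORA 2.0.
- **The rule.** The decision rule comes earlier in the same section, under the primary outcome: "Difference in primary outcome among the two vaccine arms will be assessed by a two-sided 95% confidence interval". Non-inferiority holds if the lower limit of the 95% Wald interval for second minus first lies above -10%. The anti-N sentence repeats neither the margin nor the direction.
- **Anti-N as infection.** Section 5.2 describes an infection as "identified by the presence of anti-SARS-CoV-2 nucleocapsid antibodies or SARS-Cov-2 PCR or rapid antigen test", and section 9.2.3 as "identified by the presence of anti-SARS-CoV-2 nucleocapsid antibodies, or PCR or rapid antigen test".
- **Anti-N as immune response.** Section 5.1 says the N assay is added "to gain a broader insight on the immune response of the participants".
- **The vaccines.** Section 8.1.1 describes the Moderna mRNA as "encoding the pre-fusion stabilized spike glycoprotein (S) of SARS-CoV-2 virus". Section 3.4 likewise describes Comirnaty as based on a spike antigen.
- **Timing and eligibility.** Section 9.2.2 measures anti-N "antibodies (qualitative) with the commercial Elecsys® Anti-SARS-CoV-2 tests at baseline and at 12 weeks". On previous infection, section 7.1 excludes PCR-documented infection and/or "documented antibodies less than 3 months prior to randomisation".

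**The concern.** The same laboratory result is an unfavourable clinical event in sections 5.2 and 9.2.3 and a response to be preserved in section 11.4.3. A spike-based vaccine gives no reason to expect anti-N, so a non-inferiority claim on it would present an infection marker as immunogenicity.

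Three further problems follow.

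- **Direction.** If the primary rule is carried over, more anti-N positives count in favour of the second vaccine.
- **Margin.** Ten percentage points was set against an assumed 90% response. Against a rate of a few per cent it is wider than the rate itself, so the test passes almost regardless of the data.
- **Presence is not seroconversion.** However the 3-month clause in section 7.1 is read, undocumented earlier infections can enter. They would then be counted as positive at 12 weeks.

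The ABCORA comparison carries a related risk. Section 11.4.3 names antibody classes but no antigen, and the panel in sections 5.1 and 9.2.2 covers S1, S2, RBD and N.

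**Working it through.** **Inputs.** 190 per arm, 90% reactivity in both arms, power 90% and type I error 0.025 (section 11.2); margin 10 points and the Wald rule (section 11.4.3). The documents give no expected anti-N rate, so every anti-N rate below is an assumption.

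**1. Reproduce the plan's sample size.**

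n per arm = (1.960 + 1.282)² × (0.9×0.1 + 0.9×0.1) / 0.10² = 10.51 × 0.18 / 0.01 = 189.1, rounded up to 190, or 380 in total. This matches section 11.2. Exact binomial enumeration of the Wald rule at 190 per arm gives 89.99% power.

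**2. Apply the rule to anti-N.** With p1 the first and p2 the second vaccine, and SE = √(p1(1−p1)/n + p2(1−p2)/n):

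- primary rule carried over (more is better): pass if (p2 − p1) − 1.96·SE > −0.10
- opposite direction (less is better): pass if (p2 − p1) + 1.96·SE < 0.10

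Probability of passing at 190 per arm, by exact binomial enumeration:

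| Assumed anti-N, first vs second | Primary rule | Opposite direction |
|---|---|---|
| 2% vs 2% | 1.000 | 1.000 |
| 5% vs 5% | 0.992 | 0.992 |
| 2% vs 4% | 1.000 | 0.987 |
| 5% vs 2% | 0.939 | 1.000 |
| 5% vs 10% | 1.000 | 0.471 |
| 5% vs 15% | 1.000 | 0.030 |
| 10% vs 2% | 0.160 | 1.000 |

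Three rows show the mechanism, with the assumed rates put in as if observed:

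- 5% vs 5%: SE = √(2×0.05×0.95/190) = 0.0224. The limits are ±4.4 points, well inside 10 on either side.
- 5% vs 15%: SE = √((0.0475 + 0.1275)/190) = 0.0303. The interval is +4.1 to +15.9 points. The primary rule passes; the opposite direction fails.
- 10% vs 2%: SE = √((0.09 + 0.0196)/190) = 0.0240. The interval is −12.7 to −3.3 points. The primary rule fails, although the second arm has one fifth of the positives.

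**3. A bound that needs no second-arm rate.** The lower limit is worst when the second arm has no positives.

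- First arm 12/190 = 6.3%: −0.0632 − 1.96×√(0.0632×0.9368/190) = −0.0977. The rule is met for every second-arm count from 0 to 190.
- First arm 13/190 = 6.8%: −0.0684 − 1.96×√(0.0684×0.9316/190) = −0.1043. Failure first becomes possible.

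**4. Higher equal rates.** The pass probability is 0.900 at 10%, 0.779 at 15% and 0.686 at 20%. The test is then no longer automatic.

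**5. Number actually randomised.** The Protocol (third sub-protocol), section 7.1, reports 430 randomised. Assuming 215 per arm: 5% vs 5% gives 0.996/0.996, 5% vs 15% gives 1.000/0.031, and 10% vs 2% gives 0.167/1.000. The picture does not change.

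**The case against.** The strongest reply is that a rule does exist. Section 11.1 frames the hypothesis for serological immune response in general, no worse by more than 10%, and section 11.4.3 then uses the same term with the same order of vaccines for anti-N. That is a natural reading, but it does not rescue the analysis: the rule it supplies rewards more anti-N, against sections 5.2 and 9.2.3.

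Other points stand in part.

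- **Rates.** The automatic pass depends on low positivity, which the documents neither state nor rule out. Admitting older infections would push the rate up. The direction conflict remains at any rate.
- **Large gaps.** The 5% vs 15% and 10% vs 2% cases show how the rule behaves; they are not predictions. No document supports gaps of that size between randomised arms.
- **Some information.** Read with lower as better, a pass does bound the second vaccine's excess at 10 points. At rates near 5% that bound is too loose to be useful.
- **Already reported.** Section 11.4.3 gives immunological outcomes by arm at baseline and 12 weeks, and clinical outcomes by arm. Baseline positivity would therefore be visible. Two separate percentages still do not identify who seroconverted.
- **Master protocol.** Analysis populations, missing data and deviations are deferred to it, and it was not available. Its treatment of baseline positives cannot be judged, but section 11.4.3 does not refer to it for the anti-N comparison.

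**Conclusion.** The concern holds. As written, the plan puts an infection marker through a test designed for a vaccine response.

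The conflict between sections rests on the text alone. The size of the effect rests on assumed anti-N rates: at 5% or below in both arms, a pass under either direction is close to certain (0.992 or more at equal rates). With up to 12 of 190 positive on the first vaccine, the carried-over rule cannot fail. Where the arms differ widely, that rule passes the second vaccine when it has more positives and tends to fail it when it has far fewer.

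The effect is confined to a secondary or tertiary analysis. The primary anti-S comparison and the sample size of 380 stand, and infection outcomes are reported separately. It should be corrected because the result, if published as planned, would be misread as immunogenicity.

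**What to change.** In section 11.4.3:

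- Remove anti-N from the non-inferiority analyses.
- Report anti-N seroconversion (negative at baseline, positive at 12 weeks) by arm, with a 95% CI for the difference, as an infection outcome where lower is better.
- Use it to flag infected participants in a sensitivity analysis of the primary anti-S endpoint.
- State the antigens for the ABCORA non-inferiority analysis. S1, S2 and RBD fit its purpose; N does not.

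The cost is small: one sentence reworded, one further summary and one sensitivity analysis. Anti-N is already measured at both time points, so no new data are needed and the primary analysis does not change.

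Section 7.1 of the Protocol (third sub-protocol) describes this trial as conducted, so the change now concerns the analysis record and reporting. If the planned comparison has been run, present it as an infection marker and record the change as a deviation.
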